# PLANS FOR SUBJECTS AT THE END OF THE PROTOCOL

Subjects will return to the standard of care at the end of the protocol. Subjects who are interested in starting PrEP will be linked to care with a community provider.

# CLINICAL SITE MONITORING AND RECORD AVAILABITLITY

The Emory University IRB, the OHRP, FDA, or other government regulatory authorities may perform clinical site monitoring. Clinical research sites monitoring may include the review of the individual participant records, including consent forms, CRFs, supporting data, laboratory specimen records, and medical records (physicians' progress notes, nurses' notes, individuals' hospital charts) to ensure protection of study participants, compliance with the protocol, and accuracy and completeness of records. The monitors may also inspect sites' regulatory files to ensure that regulatory requirements are being followed.

The investigators will make study documents (e.g., consent forms, CRFs) and pertinent hospital or clinic records readily available for inspection by the local IRB or the OHRP for confirmation of the study data.

# ADVERSE EVENT MONITORING AND REPORTING

Adverse events (AEs) will be reported on an expedited basis at the standard level during the protocol-defined expedited adverse event (EAE) Reporting Period, which is the entire study duration for an individual subject (from study enrollment until study completion or discontinuation of the subject from study participation for any reason).

# AE Reporting

Any AE that is reported to either the investigators or their designated research associates by a study subject or by medical staff caring for the subject and which meets the criteria will be documented.

In addition, clinical investigators will monitor subjects for Serious adverse events (SAE) Unanticipated problems (UP) during each study visit. Any SAE that is judge related to study product or UP will be reported to the IRB within 5 days of the event. The standard Emory IRB reporting guidelines for AE and SAE reporting, as documented at http://www.emory.edu/IRB/guidelines\_adverse\_event.php, will be followed.

A SAE is an adverse drug experience that results in any of the following outcomes:

- 1. Death.
- 2. Life-threatening situation The subject was at risk of death at the time of the adverse event/experience. It does not refer to the hypothetical risk of death if the AE were more severe or were to progress.
- 3. Inpatient hospitalization or prolongation of existing hospitalization.
- 4. Persistent or significant disability/incapacity Any AE having an outcome that is associated with a substantial disruption of the ability to carry out normal life

functions, including the ability to work. This is not intended to include transient interruption of daily activities.

- 5. Congenital anomaly/birth defects Any structural abnormality in subject's offspring that occurs after intrauterine exposure to treatment.
- 6. Important medical events/experiences that may not result in death, be lifethreatening, or require hospitalization may be considered a serious adverse event/experience when, based upon appropriate medical judgment, they may jeopardize the subject and may require medical or surgical intervention to prevent one of the outcomes listed above, i.e., death, a life-threatening adverse event/experience, inpatient hospitalization or prolongation of existing hospitalization, a persistent or significant disability/incapacity, or a congenital anomaly/birth defect. Examples of such medical events/experiences include allergic bronchospasm requiring intensive treatment in an emergency room or at home, blood dyscrasias or convulsions that do not result in inpatient hospitalization, or the development of drug dependency or drug abuse.
- 7. Spontaneous and elective abortions will be reported to the Emory IRB as serious adverse events.
- 8. Severity of AEs will be rated according to the following definitions:
- Mild: The adverse event is transient and easily tolerated by the subject.
- Moderate: The adverse event causes the subject discomfort and interrupts the subject's normal activities.
- Severe: The adverse event causes considerable interference with the subject's normal activities and may be incapacitating or life-threatening.

The following definitions will be used to assess the relationship of the AE to study drugs or procedures:

Probably Related: An adverse event has a strong temporal relationship to study drug or recurs on re-challenge, and another etiology is unlikely or significantly less likely.

Possibly Related:	An adverse event has a strong temporal relationship to the study drug, and an alternative etiology is equally or less likely compared to the potential relationship to study drug.
Probably Not Related:	An adverse event has little or no temporal relationship to the study drug and/or a more likely alternative etiology exists.
Not Related:	An adverse event is due to an underlying or concurrent illness or effect of another drug and is not related to the study drug (e.g., has no temporal relationship to study drug or has much more likely alternative etiology).

If the adverse event is in, the investigator's opinion, possibly or probably related, or not related to study drug or procedures, then an alternate etiology will be provided by the investigator.

It should however be noted that a severe adverse event /experience is not necessarily serious, as the term severe is a measure of intensity while a serious adverse event (SAE) is determined based on the aforementioned regulatory criteria.

All AEs and laboratory abnormalities will be graded according to the Division of AIDS Table for Grading the Severity of Adult and Pediatric Adverse Events (DAIDS AE Grading Table), Version 1.0, December 2004, which can be found on the DAIDS RCC Web site: http://rcc.tech-res.com/tox\_tables.htm.

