# Rectal biopsy procedures

[name] or [name] FNP will be performing all rectal biopsies utilizing a disposable rigid sigmoidoscope, light source, and jumbo biopsy forceps. [name] was trained in office based rectal biopsy procedures by [name], an experienced gastroenterologist at Emory University, and [name] trained [name]. All biopsy procedures will be performed in an examination room at the Hope Clinic with assistance from the project coordinator or clinical research nurse. Similar procedures have been performed by [name] or [name] >200 times for other research protocols with no complications. Briefly, without the administration of any previous enemas or other preparation, 8-12 adequate ~1.0 mm thick biopsy specimens will be taken from normal-appearing rectal mucosa 10 cm above the external anal aperture using a rigid sigmoidoscope and flexible sigmoidoscopic forceps mounted on a semi-flexible rod. All biopsy specimens will be coded with a unique numeric identifier such that the CDC laboratories that receive the specimens will be unable to link them back to

the study participants. Specimens will be transported directly to CDC after the study visit.

Twenty-four to forty-eight hours after the procedure, study personnel will contact the subjects who donated rectal biopsy samples and inquire about symptoms, complications, or adverse events related to study procedures. Subjects who report symptoms suggestive of any significant complications will receive advice on seeking care, and will be given referrals to appropriate healthcare professionals as needed. This follow-up may be completed over the phone or through electronic communication.

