# DATA SAFETY MONITORING

Summaries of adverse events (Grades 3 or 4), and targeted AEs across study groups as well as study conduct will be reviewed regularly (in real time and summarized quarterly) by study investigators. Any SAE that is judge related to study product or UP will be reported to the IRB within 5 days of the event. The standard Emory IRB reporting guidelines for AE and SAE reporting, as documented at http://www.emory.edu/IRB/guidelines\_adverse\_event.php, will be followed.

Additional safety monitoring will be performed annually by an independent Medical Safety Monitor. Based on the 1 year accrual expectation for the study, it is anticipated that the study will undergo 2 reviews by the Medical Safety Monitor. The first will occur approximately 6 months after the accrual of the first subject. The safety report will summarize AEs and SAEs by study group. The DCC will work with the Medical Safety Monitor to complete a 'final assessment' following the review of each safety report. As part of the final assessment the Medical Safety Monitor will conclude 'the study can continue as no safety concerns have been identified at the time of the review' or 'the study cannot continue as currently designed'. The final assessment by the Medical Safety Monitor will be provided to the study PI who will make the findings available as appropriate to the Emory IRB and the NIH.

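### The protocol records adverse events against criteria it never states and actively monitors at visits only for serious events and unanticipated problems, so capture of non-serious drug effects is neither defined nor solicited

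*Protocol*

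**What the plan says.** The duty to document is set in the protocol's AE Reporting section. An event that reaches the investigators or their research associates "by a study subject or by medical staff caring for the subject and which meets the criteria will be documented". The next paragraph sets the active part: "clinical investigators will monitor subjects for Serious adverse events (SAE) Unanticipated problems (UP) during each study visit". The section then defines serious events: "A SAE is an adverse drug experience that results in any of the following outcomes".

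Other text expects a wider net:

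- Adverse Event Monitoring and Reporting: "Adverse events (AEs) will be reported on an expedited basis at the standard level", for the whole of each man's time on study.
- AE Reporting, later paragraphs: mild, moderate and severe are defined, relatedness to study drug is assessed, and every adverse event and laboratory abnormality is to be graded on the DAIDS table. The text adds that "a severe adverse event /experience is not necessarily serious".
- Data Safety Monitoring: the investigators review "Summaries of adverse events (Grades 3 or 4), and targeted AEs across study groups". The Medical Safety Monitor receives a report of adverse events and, separately, serious adverse events by study group.

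After a biopsy, staff contact the participant at 24 to 48 hours to "inquire about symptoms, complications, or adverse events related to study procedures". The SAP contains no adverse-event analysis.

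**The concern.** Grading and tabulation act on what has already been written on a form. If the rule for what goes on the form is undefined, and nobody asks about ordinary drug effects, the tables downstream can be thin for reasons unrelated to the products.

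Two consequences follow. First, the Medical Safety Monitor must conclude from the by-arm report whether the study can continue. A report with few non-serious events could mean good tolerability or poor capture, and the reader could not tell which. Second, no blinding is described, and men in Phases II and III have their assignment reviewed and are handed a named product. What they volunteer can depend on what they expect of that product, so the contrast between arms is open to reporting bias.

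This matters more than it would for two long-used regimens. The Abstract and Lay Summary give side effects of current tenofovir-based regimens as the reason newer agents are being developed, and Risk of Genvoya says that product has had no trials for pre-exposure prophylaxis.

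**Working it through.** The plan has no figure to reproduce here. The check is mainly textual, followed by an illustration of scale.

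**Step 1: what are the criteria?** The documenting sentence does not name them. In the same section the only event criteria are the serious-event outcomes. The one later use of the word, "a serious adverse event (SAE) is determined based on the aforementioned regulatory criteria", points to that same list. No criterion for a non-serious adverse event appears in either document.

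**Step 2: which contacts would ask a man about a non-serious drug effect?**

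| Contact (protocol section) | What is asked or monitored | Nausea or diarrhoea from study drug? |
|---|---|---|
| Each study visit (AE Reporting) | Serious events and unanticipated problems | Not unless serious or an unanticipated problem |
| 24 to 48 h after biopsy (Rectal biopsy procedures) | Symptoms, complications and events tied to study procedures | Not as such |
| Symptom query at visits (resistance paragraph after Risk of Genvoya) | Acute HIV signs: fever, fatigue, malaise, rash, swollen glands, ulcers, muscle or joint pain | No, though fatigue, malaise or rash could surface |
| Phone, text and email contacts (Phone calls/retention contacts) | Retention and adherence | No |

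Nausea is named as a drug effect under Risks of Truvada for PrEP, and nausea and diarrhoea under Risk of Genvoya. No row asks about them routinely.

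**Step 3: what do later sections need?** The Grade 3 or 4 summary needs severe events that are not serious. The Medical Safety Monitor's report needs adverse events as well as serious ones. Both presuppose capture that Steps 1 and 2 do not secure.

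**Step 4: how many events could be affected?** Inputs:

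- Dosed per arm: 20 in Phase II plus 20 in Phase III = 40. Men may enter more than one phase, so this counts dosing courses and not necessarily distinct men.
- Nausea: 9% on Truvada and 5% on placebo, from Risks of Truvada for PrEP. No nausea incidence is given for Genvoya, so applying this range to both arms is an assumption.
- Non-completion: about 20%, from Study Population. 40 × 0.80 = 32.

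Formulas: expected cases = n × p; probability of at least one = 1 − (1 − p)^n.

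| n per arm | p | Expected cases | P(at least one) |
|---|---|---|---|
| 40 | 0.05 | 2.0 | 1 − 0.95^40 = 0.87 |
| 40 | 0.09 | 3.6 | 1 − 0.91^40 = 0.98 |
| 32 | 0.05 | 1.6 | 1 − 0.95^32 = 0.81 |
| 32 | 0.09 | 2.9 | 1 − 0.91^32 = 0.95 |
| 20 (Phase III only) | 0.05 | 1.0 | 1 − 0.95^20 = 0.64 |
| 20 (Phase III only) | 0.09 | 1.8 | 1 − 0.91^20 = 0.85 |

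Half of the 40 courses are a single dose, so rates from trials of pre-exposure prophylaxis may overstate what would be seen. The table shows how many events of one common type could turn on the undefined rule. It does not estimate how many would be missed.

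**The case against.** The best reply is that the protocol's intent is clear. The documenting sentence speaks of any adverse event, and the serious-event monitoring is introduced as an addition to it. Mild and moderate grades are defined, all adverse events are graded, and the safety report lists adverse events beside serious ones. The section also cites institutional guidelines for reporting both kinds, which are not available here and may contain criteria.

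Much of this stands. A reader might infer that the unstated criteria are the serious-event outcomes, so that every non-serious event is lost and the documented count is about zero. No sentence says so, and that reading would leave the grading and reporting provisions largely empty. A reader might also infer that only a hospitalised man would be counted. That is wrong even on the narrow reading, because the list also covers life-threatening events, disability and important medical events without hospitalisation. Nor is all capture spontaneous: visits, the post-biopsy contact and the HIV symptom query each solicit something, and a drug symptom could emerge in passing.

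It is also fair that tolerability is not the study's goal, which is compartment pharmacokinetics and mucosal inflammatory effects, and that the SAP plans no tolerability comparison.

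What the reply does not supply is a working rule. Provisions for grading and summarising do not tell a coordinator what to record when a man mentions nausea, and do not require anyone to ask. The institutional guidelines are cited for reporting; the documenting sentence does not refer to them.

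**Conclusion.** The point holds in a limited form. The threshold for documenting an adverse event is undefined, and no stated contact systematically asks about non-serious drug effects. This fits poorly with the grading of all adverse events, the Grade 3 or 4 summary and the by-arm safety report. The by-arm summary may therefore be incomplete, and it depends partly on what men who know their product volunteer. The documents do not establish that non-serious events would be excluded, or how many would be missed.

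The size is illustrative: 2.0 to 3.6 nausea cases per 40 dosing courses in an arm, or 1.6 to 2.9 after 20% non-completion. This assumes that the protocol's 5% to 9% figures carry over to short dosing and to both products. Because safety comparison is not the stated goal, this is a worthwhile, inexpensive improvement. It does not threaten the study's main analysis.

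**What to change.** Three changes to the protocol:

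1. In AE Reporting, delete the clause that makes documentation depend on meeting criteria. State that every adverse event, serious or not, is documented with onset date, grade and relatedness.
2. Extend the existing visit check from serious events and unanticipated problems to all adverse events. Use the same non-leading question in both arms at each existing post-dose visit: visits 2 and 3 in Phase II, visits 3 and 4 in Phase III. At Phase II visit 2 the question belongs with the sampling 4 to 6 hours after the dose.
3. Widen the existing 24 to 48 hour post-biopsy contact to cover drug effects as well as procedure effects.

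The cost is a few more minutes at visits and more adverse-event form entries. No new visit, procedure or staff is needed. A neutral question reduces the dependence on volunteered reports but does not remove the influence of knowing one's product, so the by-arm summary should still be read as open-label.

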# DATA SAFETY MONITORING

Summaries of adverse events (Grades 3 or 4), and targeted AEs across study groups as well as study conduct will be reviewed regularly (in real time and summarized quarterly) by study investigators. Any SAE that is judge related to study product or UP will be reported to the IRB within 5 days of the event. The standard Emory IRB reporting guidelines for AE and SAE reporting, as documented at http://www.emory.edu/IRB/guidelines\_adverse\_event.php, will be followed.

Additional safety monitoring will be performed annually by an independent Medical Safety Monitor. Based on the 1 year accrual expectation for the study, it is anticipated that the study will undergo 2 reviews by the Medical Safety Monitor. The first will occur approximately 6 months after the accrual of the first subject. The safety report will summarize AEs and SAEs by study group. The DCC will work with the Medical Safety Monitor to complete a 'final assessment' following the review of each safety report. As part of the final assessment the Medical Safety Monitor will conclude 'the study can continue as no safety concerns have been identified at the time of the review' or 'the study cannot continue as currently designed'. The final assessment by the Medical Safety Monitor will be provided to the study PI who will make the findings available as appropriate to the Emory IRB and the NIH.

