**Design:** To address the efficacy of the new formulated anti-HIV agents and their ability to penetrate the mucosal tissues in MSM, investigators at Emory University will collaborate with the Centers for Disease Control and Prevention (CDC) to conduct a randomized clinical trial of 90 MSM. Men will be randomized into a 2-arm study (fortyfive men assigned to each arm) as follows: (Arm 1) daily oral Truvanda® or (Arm 2) daily oral Genvova®. Each study arm includes 3 phases: (1) pre-drug, (2) short-course, and (3) steady state. For phase I, there will be 5 men assigned to both arm 1 and arm 2. Phases II and III will each have 20 men assigned to both arms. The study will entail 2 study visits for phase I, 3 study visits for phase II, and 4 study visits for phase III at the Emory University Hope Clinic. During phase I: visit 1, all men will be screened for eligibility and undergo written informed consent, physical examination, rapid HIV testing, phlebotomy for screening laboratories, and randomization. During study visit 2 (time 1-6 weeks after study visit 1), participant returns and a urethral swab, 2 pre- wet penile swabs, and a urine sample will be collected. Participant will then undergo a rectal biopsy via rigid sigmoidoscopy for establishment of baseline values. During phase II: study visit 1, men will be screened for eligibility and undergo written informed consent, physical examination, rapid HIV testing, phlebotomy (will collect 4 tablespoons) for screening laboratories, and randomization. During study visit 2 (time 1-6 weeks after study visit 1), men will be dispensed and instructed to take either one dose of Truvada® or Genvoya®. After 4 to 6 hours after dosing, a urethral swab, 2 pre- wet penile swabs, 4 tablespoons of blood, and a urine sample will be collected. During study visit 3 (time 24 hours after drug dosing), men will return after 24 hours of study product use for repeat phlebotomy, urethral and penile swabs, collection of urine and rectal secretions, and rectal biopsy via rigid sigmoidoscopy. For phase III: visit 1,

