For this protocol, we will recruit HIV-negative MSM and TGW who are not on hormone therapy aged 18-49 and who are willing to adhere to study procedures. There will be 3 phases, with 2 study visits for phase I, 3 study visits for phase II, and 4 study visits for phase III that will be conducted over a maximum period of 12 weeks. Participants are allowed to participate in more than one phase if a recovery or washout period occurs 8 weeks in between each phase. The first visit for all phases (phase I, phase II, and phase III) will be a screening visit where eligibility is determined, written informed consent is obtained, screening tests are performed, and men will be randomized to one of two study groups: 1. Use of oral Truvada®; or 2. Use of oral Genvoya®. During the second study visit (visit 2), men in phase I will not receive product, but will come in for blood work, urine sample, 2 pre-wet penile swabs, urethral swab, rectal swab, and rectal biopsy sampling. Participants who are in phase II will receive a single dose of the study product during visit 2, 1-6 weeks after the screening visit. MSM will return 4 to 6 hours after taking the drug for a urine sample. We will then collect 4 tablespoons of blood from the participants arm, in addition to, 2 pre-wet penile swabs, and a urethral swab. The third study visit will occur 24 hours from dosing time for MSM in phase II. Men will undergo a blood draw, urine sample, penile, urethral, and rectal swab, and rigid sigmoidoscopy for collection of rectal secretions and biopsies. Participants in phase III at study visit 2 will receive a 10-day supply of the study drug and will be instructed to take it for 10 consecutive days. For visit 3 in phase III, participants will return for a blood draw, urine collection, 2 pre-wet penile swabs, and a urethral swab to examine drug levels after 3-5 days of taking study drug. They will then return 10 days from dosage for visit 4, where blood, urine, penile, urethral, and rectal swabs will be collected, and rectal biopsy sampling will occur. All specimens will be transported directly to the laboratory of [name] at CDC where multiple immune assays are planned to determine the ability of these agents to penetrate mucosal tissues and potentially prevent HIV infection during RAI exposure.

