# Phase II

40 participants (20 in each study arm) will be enrolled in study phase 2.

Study visit 2 will occur 1-6 weeks after the screening visit. During visit 2, the study group assignment will be reviewed and participants will be provided with a single dose of Truvada® or Genvoya®. Drug will be dispensed through the Emory Investigational Drug Service. Depending on the study arm they were assigned to, MSM will be dispensed 1 day of Truvada® or Genvoya® and instructed on dosing for that day. Four to six hours after the drug is taken, a urine sample, 4 tablespoons of blood will be drawn from the participants arm, as well as, penile and urethral swabs will be collected from participants. These sample will be used at CDC to develop an assay to detect Truvada® and Genvoya® in the body. All specimens will be coded with a unique numeric identifier such that the CDC laboratories that receive the specimens will be unable to link them back to the study participants. Participants will be requested to abstain from receptive anal intercourse 3 days prior to study visit 2 and while taking study product.

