# Phase III

40 participants (20 in each study arm) will be enrolled in study phase 2.

Study visit 2 will occur 1-6 weeks after the screening visit. During visit 2, the study group assignment will be reviewed and participants will be provided with a 10 day supply of Truvada® or Genvoya®. Drug will be dispensed through the Emory Investigational Drug Service. Depending on the study arm they were assigned to, MSM will be dispensed 10 days of Truvada® or Genvoya® and instructed on dosing for 10 consecutive days prior to their scheduled study visit 4. MSM will be requested to abstain from receptive anal intercourse while on study product. Participants will be scheduled to return for their third study visit after taking the study product for 3-5 consecutive days.

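### Adverse events are summarised by study group, so each arm combines undosed, single-dose and ten-day men; a rate on the arm total would show an excess confined to ten-day dosing at 44% of its size

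*Protocol*

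**What the plan says.** Two safety summaries are described in the protocol under Data Safety Monitoring, and both are organised by study group. For the investigators: "Summaries of adverse events (Grades 3 or 4), and targeted AEs across study groups as well as study conduct will be reviewed regularly". For the independent Medical Safety Monitor: "The safety report will summarize AEs and SAEs by study group". After each report the Monitor concludes either that the study can continue or that it cannot continue as designed.

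The protocol uses study group for the drug assigned. The Lay Summary says "men will be randomized to one of two study groups" and names them as oral Truvada and oral Genvoya. Under Visit 2, Phase II, "the study group assignment will be reviewed and participants will be provided with a single dose". The Phase III paragraph uses the term in the same way. Levels of exposure are called phases.

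The Abstract has "fortyfive men assigned to each arm", divided over three phases:

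- Phase I: "For phase I, there will be 5 men assigned to both arm 1 and arm 2". The Lay Summary adds that "men in phase I will not receive product".
- Phase II: 20 men per arm, one dose.
- Phase III: 20 men per arm; "participants will be provided with a 10 day supply".

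Neither document divides safety data by phase, length of dosing or drug actually taken. The SAP contains no safety analysis.

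**The concern.** Followed as written, the rule gives one summary per drug, and each covers three very different exposures. Two things follow.

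First, if an event rate is computed on all the men in an arm, an effect that needs repeated dosing is averaged over 25 men who could not have shown it. The ten-day course is the highest exposure in the study, and the section on risks of Genvoya says that this drug has had no trials for pre-exposure prophylaxis. It is the cell a safety reader would most want to see alone.

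Second, an event in a Phase I man appears under the drug he was randomised to, although he took none of it.

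At stake is how clearly the Monitor and the investigators can read event rates, chiefly for events that are not serious or not judged related, since these have no separate reporting route.

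**Working it through.** **Inputs.** Per arm: 5 in Phase I, 20 in Phase II, 20 in Phase III (Abstract). Expected non-completion: about 20% overall (Study Population). Nausea: 9% on Truvada against 5% on placebo (Risks of Truvada). The documents give no event rates by phase, so the rates used below are assumptions.

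**The plan's own figures.** 5 + 20 + 20 = 45 per arm; 2 × 45 = 90; 90 × (1 − 0.20) = 72 completers. All three agree with the protocol.

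**Dilution on the arm total.** Let r be the single-dose rate as a fraction of the ten-day rate, with no Phase I events. Then

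factor = pooled rate / ten-day rate = (20 + 20r)/45.

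| r | factor |
|---|---|
| 0 (ten-day dosing only) | 20/45 = 0.444 |
| 0.125 | 22.5/45 = 0.500 |
| 0.25 | 25/45 = 0.556 |
| 0.50 | 30/45 = 0.667 |
| 1 | 40/45 = 0.889 |

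As an assumed example with r = 0, 4 of 20 ten-day men (20%) becomes 4/45 = 8.9%.

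**With a background rate.** Assume 9% nausea in ten-day men and 5% in the other 25. The pooled rate is (20 × 9% + 25 × 5%)/45 = 6.8%, which is 75% of 9%. The excess over background falls from 9 − 5 = 4.0 points to 6.8 − 5 = 1.8 points, a factor of 20/45 = 0.444. So with a background rate it is the excess that shrinks to 44%; the displayed rate shrinks less.

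**Biopsy events.** Every phase ends with a rectal biopsy, so all 45 men in an arm are planned to be at risk and there is no dilution.

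**Sensitivity for r = 0.**

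- 20% dropout in every phase: 16/36 = 0.444, unchanged.
- 20% dropout in Phase III only: 16/(16 + 25) = 16/41 = 0.39.
- Five Phase II men per arm also enter Phase III and each man is counted once: 20/(45 − 5) = 0.50.

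**With separate columns.** The ten-day rate has its own denominator of 20 per arm (16 after 20% dropout), and the factor is 1.

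**The case against.** The strongest reply is that the plan never says it will compute pooled rates. The section states no denominator and no layout, and it does not rule out rows by phase within each drug. That stands, and it is why the dilution is conditional. It does not remove the point: the only grouping the section names is the randomised drug, and nothing elsewhere adds exposure.

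A reader might infer that undosed men's events are recorded as drug reactions. The documents do not support this. The AE Reporting section has each event's relationship to study drugs or procedures graded, so such an event could be graded not related. It would still be listed under that drug.

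A reader might also infer that a serious signal would be hidden. That goes too far. Four events remain four events in any table, the Monitor's decision has no rate threshold, the investigators review in real time as well as quarterly, and serious events judged related to study product go to the IRB within five days.

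Nor is one drug favoured. Both arms have the same planned 5/20/20 mix, so pooling shrinks absolute rates and differences without changing the direction of the comparison.

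Finally, one might suppose that the first Monitor report will hold few or no ten-day men, or that a rate will fall between reviews because the mix has changed. The documents do not give the order in which phases fill, so this is speculation.

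**Conclusion.** The point holds as a weakness in how safety data are grouped. As written, each arm's summary mixes no drug, one dose and ten days, and lists undosed men under a drug. If rates use the arm total, the excess of a toxicity confined to ten-day dosing is shown at 44% of its size. With no Phase I events the factor rises to 0.67 when the single-dose rate is half the ten-day rate and to 0.89 when they are equal.

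These figures assume 45 different men per arm and the same dropout in each phase. It is tempting to say that any ten-day toxicity would appear at less than half its true rate. That needs a single-dose rate below 12.5% of the ten-day rate and a negligible background, and the documents give no figures to show either.

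**What to change.** Amend the Data Safety Monitoring section so that the investigators' summaries and the Monitor's report both:

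- tabulate adverse events and serious adverse events by arm within exposure level (single dose, ten days), with the number dosed as the denominator and counts beside percentages;
- show the Phase I men of both arms (5 + 5 = 10) as one undosed, procedures-only group;
- count a man who enters more than one phase, which the Abstract permits after at least 8 weeks, in each phase he enters, and assign each event to the phase in which it occurred.

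No new data are needed, because arm and phase are known for every participant. The cost is slightly longer tables and smaller cells: with 20 men in a cell one event moves the percentage by 1/20 = 5 points, which is why counts should stand beside it.
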